10.5.2 Safety Evaluation

For all safety analyses, the Safety population will be used. The assessment of safety will be based mainly on the frequency of AEs and on the number of laboratory values that fall outside of pre-determined ranges. Other safety data (i.e., ECG, vital signs) will be considered as appropriate.

For all safety analyses, the safety population will be used. The assessment of safety will be based mainly on the frequency of AEs and on the number of laboratory values that fall outside of pre-determined ranges. Other safety data (i.e., electrocardiogram, vital signs) will be considered as appropriate.

Adverse events will be summarized by presenting the number and percentage of patients having any AE, having an AE in each body system and having each individual AE. Any other information collected (e.g., CTC grades or relatedness to study drug) will be listed as appropriate. In addition, the incidence of pneumonitis AEs will be summarized by preferred term.

Deaths reportable as SAEs and non-fatal SAEs will be listed by patient and tabulated by the type of AE.

Laboratory data will be summarized by presenting shift tables using CTC grades (screening to most extreme post-screening value), by presenting summary statistics of raw data and change from baseline values (means, medians, standard deviations) and by the flagging of CTC grades in data listings.

Data from other tests (e.g., electrocardiogram or vital signs) will be listed and any other information collected will be listed as appropriate.

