7.5 Demographic and Baseline Characteristics

Demographic data including date of birth, sex, race and ethnicity will be collected at Screening Visit 1a. Age will be derived as the age in years at Screening Visit 1a. Age, sex, race, ethnicity, height, weight, BMI and Karnofsky Performance Status will be summarized for the ITT population. In the event of a difference between the safety and ITT populations, this summary of demographic data will be repeated for the safety population.

The date of informed consent, any failed inclusion or exclusion criteria and the source of subject referral will be listed only.

Relevant medical history and current medical conditions are collected at Screening Visit 1a. The number of patients with at least one relevant medical history or current medical condition and at least one active problem will be presented and a summary will also be provided of the medical history by body system and preferred term. These summaries will be performed on the ITT population.

A pregnancy test is performed at Screening Visit 1a and Baseline Visit 1b and the data collected will be listed only. If any unscheduled pregnancy tests are performed during the treatment or follow-up periods of the study these data will also be listed.

Each patient's prior antineoplastic therapy is recorded at Screening Visit 1a. The number of patients taking each therapy type overall and by setting will be presented along with the total number of separate courses of therapy. Each separate record entered on the CRF will be counted as a separate course of therapy. For each therapy type/setting combination the overall best response per patient will be determined as either Complete Response (best), Partial Response, Stable Disease, Complete Response (unconfirmed), Unknown, Not Applicable or Progressive Disease (worst). The total duration of time per therapy type/setting will be calculated for each patient based on the CRF data. It is expected the duration will be calculated in months and should take into account any overlap in dates recorded on the CRF. See Section 7.2.2 regarding the handling of partial dates. Summaries of prior antineoplastic therapy will be performed on the ITT population, and in the event of a difference between the safety and ITT populations will be repeated for the safety population.

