8.3 Laboratory Tests

Each hematology, blood chemistry and serum lipid parameter will be summarized at the Baseline visit (Visit 1a), each cycle, the End of Treatment visit (last assessment up to and including 30 days after last dose date, including unscheduled assessments). The change from baseline will be presented at all post-baseline visits where this can be calculated.

Each coagulation parameter is collected at Screening Visit 1a and Day 1 of Cycle 2. These data will be listed.

Each urinalysis parameter will be collected at Screening Visit 1a and subsequently as clinically required. These data will be listed.

The hematology parameters collected are:

White blood cells (WBC), hemoglobin, hematocrit, platelets

Either: absolute neutrophils, absolute lymphocytes, absolute eosinophils, absolute basophils and absolute monocytes

Or: percentage neutrophils, percentage lymphocytes, percentage eosinophils, percentage basophils and percentage monocytes

The CRF allows for "other" differential counts to be recorded. These results will be listed only.

The blood chemistry parameters collected are:

Urea, blood urea nitrogen, creatinine, lactate dehydrogenase (LDH), total protein, fasting glucose, phosphorus, serum calcium, serum corrected calcium (calculated at baseline only), electrolytes (sodium, magnesium, chloride, and potassium), total bilirubin, gamma-glutamyl-transferase (GGT), albumin, alkaline phosphatase, alanine aminotransferase (ALT) (or SGPT), aspartate aminotransferase (AST) (or SGOT), uric acid

The serum lipid parameters collected are:

Total cholesterol, triglycerides, low-density lipoprotein (LDL), high-density lipoprotein (HDL)

The coagulation parameters collected are:

Prothrombin time (PT), International normalized ratio (INR)

All laboratory test results will be converted into Standard International (SI) Units by Data Management. Summary tables will present the results in SI Units.

The normal ranges for each parameter will also be included on the database so results can be calculated as being below, within or above the normal range.

Laboratory results will be graded using the Common Toxicity Criteria for Adverse Events (CTCAE) v3.0 document for each parameter where a CTC grade is defined. The parameters with grades defined are:

Hematology: WBC, hemoglobin, platelets and absolute neutrophils

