Blood Chemistry: Creatinine, fasting glucose, sodium, magnesium, potassium, albumin, bilirubin, GGT, SGOT (AST), SGPT (ALT) and alkaline phosphatase

Serum Lipid Profile: total cholesterol, triglycerides

A shift table will be presented showing the change from screening to most extreme post-screening value (including the End of Treatment visit and any unscheduled assessments) in CTC grading.

In the event that an unscheduled laboratory test is performed the data from this test will be listed. Unscheduled visit results will only be summarized if the unscheduled visit supersedes the scheduled visit's results. I.e. if a scheduled visit is missed, or the laboratory sample is not taken, or there are no results from the laboratory sample, but there is an unscheduled visit occurring prior to the next scheduled visit then the results from the unscheduled visit should be used instead.

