8.4 Vital Signs

Body temperature, pulse rate, systolic and diastolic blood pressure will be collected at Screening Visit 1a, Baseline Visit 1b, day1 of each cycle and the End of Treatment visit. Height and weight will be collected at Screening Visit 1a only. The vital signs data, including any unscheduled assessments, will be listed.

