8.5 Other Safety Assessments

The Karnofsky Performance Status will be assessed at Screening Visit 1a, Baseline Visit 1b, at day 1 of each subsequent cycle and at End of Treatment. The baseline data will be summarized as well as change from baseline for post-baseline visits. All data, including unscheduled assessments, will be listed.

Pulmonary function test (including spirometry, diffusion capacity of carbon monoxide and room air O₂ saturation at rest) will be performed at screening, as medically necessary if there is evidence of non-infectious pneumonitis, and at the end of the study. These data will be listed.

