XXXXXXXXXX/ XXXX-XXXX	Cycle 4	Yes/No	ddmmYYYY/ xx	Normal		
	Visit 8	Yes/No	ddmmYYYY/ xx	Clinically insignificant abnormality		
		Yes/No	ddmmYYYY/ xx	Clinically significant abnormality	XXXXXXXXXXXXXXXXXXXX XXXXXXXXXXXXXXXXXXXX XXXXXXXXXXXXXXXXXXXX XXXXXXXXXXXXXXXXXXXX	New or worsened Not compared Unchanged

Day is calculated relative to the day of first dose of study medication.

Programming note: Data ordered by country (alphabetically) then centre/patient identifier and visit date. Multiple clinically significant abnormality details should be listed in the order they appear on the CRF.

Listing 16.2-7.2 (page 1 of n)
Imaging
All Patients

Country/ Centre/ Patient	Visit	Date of Scan/Day	Scan Category	Location/ Site	Scan Type	Findings
XXXXXXXXXX/ XXXX-XXXX	Screening Visit 1a	ddmmYYYY/ xx	Chest, Abdomen and Pelvis	Other: xxxxxxxx	CT scan (with contrasts)	xxxxxxx
		ddmmYYYY/ xx	Brain	Other: xxxxxxxx	CT scan (with contrasts)	xxxxxxx
		ddmmYYYY/ xx	Bone	Bone		xxxxxxx
...						

Day is calculated relative to the day of first dose of study medication.

Programming note: Data ordered by country (alphabetically) then centre/patient identifier and visit date.

Listing 16.3-1.1 (page 1 of n)
 Hematology by Visit
 All Treated Patients

Country/ Centre/ Patient	Visit	Sample Date/ Day	Laboratory Number / Name	Parameter	Result (units)	CTC Grade
XXXXXXXXXX/ XXXX-XXXX	Screening Visit 1a	ddmmYYYY/ xx	XXXXXXXXXXXX/ XXXXXX	WBC	xx (unit)	Xx
				Hemoglobin	xx (unit)	Xx
				Platelets	xx (unit)	Xx
				Hematocrit	xx (unit)	
				Neutrophils	xx (unit)	Xx
				Lymphocytes	xx (unit) L	
				Eosinophils	xx (unit)	
				Basophils	xx (unit)	
				Monocytes	xx (unit) H	
				Other: xxxxx	xx (unit)	
	Baseline Visit 1b	ddmmYYYY/ xx	XXXXXXXXXXXX/ XXXXXX	WBC	xx (unit)	Xx
				Hemoglobin	xx (unit)	Xx

L=Low and H=High relative to normal ranges.
 Day is calculated relative to the day of first dose of study medication.

Programming note: Data ordered by country (alphabetically) then centre/patient identifier then by visit date. Any unscheduled assessments should be included and labeled "Unscheduled Visit".

Listing 16.3-2.1 (page 1 of n)
 Blood Chemistry by Visit
 All Treated Patients

Country/ Centre/ Patient	Visit	Sample Date/ Day	Laboratory Number / Name	Parameter	Result (units)	CTC Grade
XXXXXXXXXX/ XXXX-XXXX	Screening Visit 1a	ddmmmyyyy/ xx	XXXXXXXXXX/ XXXXXXXXXX	Urea	xx (unit)	
				BUN	xx (unit)	
				Creatinine	xx (unit) L	Xx
				LDH	xx (unit) L	
				Total Protein	xx (unit) L	

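### The laboratory shift tables have no Grade 0 screening column and let pre-dose samples count as the worst grade; SAP 8.3 also labels Visit 1a as Baseline, against most of the plan.

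*SAP*

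**What the plan says.** **Shift rule.** Protocol 10.5.2 plans laboratory summaries by "presenting shift tables using CTC grades (screening to most extreme post-screening value") and, in the same sentence, by "summary statistics of raw data and change from baseline values (means, medians, standard deviations"). SAP 8.3 repeats the first part, with a shift table "showing the change from screening to most extreme post-screening value", and includes End of Treatment and unscheduled samples.

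**Shift shells.** Tables 14.3-2.3 (hematology), 14.3-3.3 (chemistry) and 14.3-4.3 (lipids) share one layout. The columns are the Visit 1a grade: 1, 2, 3, 4, Total, Missing. The rows are the worst later grade: 0, 1, 2, 3, 4, Total, Missing.

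**Baseline label.** For hematology, chemistry and lipids, SAP 8.3 says that each parameter "will be summarized at the Baseline visit (Visit 1a), each cycle". The by-visit shells print only the word Baseline. Other parts of the SAP separate the two visits:
- 7.5: "A pregnancy test is performed at Screening Visit 1a and Baseline Visit 1b"
- 8.4: vital signs "will be collected at Screening Visit 1a, Baseline Visit 1b, day1 of each cycle"
- 8.5: Karnofsky status "will be assessed at Screening Visit 1a, Baseline Visit 1b, at day 1 of each subsequent cycle"
- Listing 16.3-1.1, for hematology itself: "Baseline Visit 1b"

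Protocol Table 9 also has 1a as Screening and 1b as Baseline (Day -7 to -1), and marks hematology, chemistry and lipids at both.

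**The concern.** This is a single-arm study, so there is no control group against which to judge change that began before treatment. Protocol 10.5.2 rests the safety assessment mainly on adverse event frequency and on laboratory values outside set ranges. In that setting a shift table should answer one question: how many patients got worse after starting the drug, and from what grade?

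The planned tables fall short in three ways.
- A patient who is normal at screening and then develops an abnormality has no column.
- A value obtained before any drug was taken can be reported as the worst grade.
- The word Baseline in the by-visit and change tables points to one visit in 8.3 and to another elsewhere, so a reader cannot tell from the output which pre-dose value is the reference.

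**Working it through.** The plan gives no figure to reproduce here. The check is a count of cells and samples, plus a comparison of text.

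**1. Shift cells.**
- Possible worsening shifts on Grades 0 to 4: 4 + 3 + 2 + 1 = 10.
- Shifts starting from Grade 0: 4 (to Grade 1, 2, 3 or 4).
- Shifts displayed with screening columns Grade 1 to 4: 3 + 2 + 1 = 6.
- Not displayed: 10 − 6 = 4, in each of the three tables.

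Each shell has six column heads and six entries per row, so a Grade 0 column was not lost when the PDF was read.

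Recovery by subtraction, for row grade k: shifts 0 to k = Total(k) − [G1(k) + G2(k) + G3(k) + G4(k)]. This works only if Total counts patients at Grade 0. The pre-printed 100% in the grand Total cell and the footnote on the denominator suggest that it does, but no shell says so.

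Platelets show the effect. Inclusion criterion 7 (Protocol 5.1) requires at least 100 x 10^9/L, and Protocol Table 3 starts Grade 2 below 75 x 10^9/L. A patient meeting the criterion is Grade 0 or 1. The shell therefore prints three columns (Grades 2 to 4) that should be almost empty and omits Grade 0.

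**2. Pre-dose samples inside the shift window.** The window opens after Visit 1a. SAP 7.1 checks on-treatment data only against the end of treatment. Adverse events, by contrast, have a first-dose limit in SAP 8.1.
- Hematology: the Cycle 1 Day 1 sample is explicitly taken before dosing (Protocol 7.6.5.1; Table 9, footnote c). With Visit 1b where drawn, that makes 1 or 2 scheduled pre-dose samples.
- Chemistry and lipids: Protocol 7.6.5.3 and 7.6.5.4 do not say whether the Day 1 sample precedes the dose. With Visit 1b, the count is 0 to 2.
- Visit 1b is uncertain for all three panels. The Table 9 grid marks it, but footnotes c, e and f and the 7.6.5 text name only screening and Day 1.

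A pre-dose sample changes a patient's cell when its grade is worse than every post-dose grade, or when there is no post-dose sample. A second route does not depend on the window: because the reference is screening, a worsening that began before first dose and then persisted is also tabulated as a shift.

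**3. Tables touched by the label conflict.** By visit: 14.3-2.1, 14.3-3.1, 14.3-4.1. Change from baseline: 14.3-2.2, 14.3-3.2, 14.3-4.2. Total 3 + 3 = 6. The three shift shells are not among them, since their columns and rows both name Screening Visit 1a.

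**The case against.** The best reply has five parts.

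- *SAP 8.3 does name a visit.* A programmer who follows that section alone uses Visit 1a, which matches the shift reference and the 7.6.5 text. This stands. A reader might infer that the laboratory baseline is undefined, or that all nine laboratory tables are ambiguous. The documents show a label conflict in six.
- *The shift rule is prespecified.* It comes from Protocol 10.5.2 and the SAP carries it over faithfully. This stands, so a change must be documented as a departure. It does not make a pre-dose value informative about the drug.
- *Nothing is lost.* Grades are listed by patient and visit in Listings 16.3-1.1, 16.3-2.1 and 16.3-3.1. This also stands: the missing column is a display gap. Even so, new-onset toxicity should not have to be derived by the reader from an unstated convention.
- *Other safeguards exist.* Clinically relevant laboratory abnormalities are also recorded as adverse events (Protocol 7.6.1 and 7.6.5), no hypothesis is tested, and PFS is untouched. This limits the severity.
- *It is late.* The SAP is marked Version 2, Final, 22 September 2017, well after the planned last visit of 30 January 2012. That is a reason to record the change and its rationale openly. It does not argue against the added column, which alters no rule.

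**Conclusion.** The point holds, at minor to moderate severity. The missing Grade 0 column is certain: 4 of 10 worsening shifts are not shown in each of three tables. The absence of a first-dose limit is also certain and is explicit for Cycle 1 Day 1 hematology. For chemistry, lipids and Visit 1b it depends on what was drawn and when. The baseline label needs reconciling in six tables.

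Three stronger readings are not supported.
- *A number of patients affected.* The documents give no rate of pre-dose worsening, so any count would rest on invented inputs.
- *A screening value that is 28 to 35 days old at baseline.* Protocol 6.6.1 gives that interval, but it labels the visit as both Visit 2 and Visit 1b. Table 9 places the screening bone scan within 3 weeks of first dose, and the screening CT limit of 35 days has no minimum.
- *Grade 0 to 1 as a main hematology shift.* Protocol 1.2.3.3 reports that early falls in counts mostly stayed within normal limits or at Grade 1. Falls within normal limits are not shifts, so this does not establish how common the shift would be.

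**What to change.** 1. Add a Grade 0 screening column to Tables 14.3-2.3, 14.3-3.3 and 14.3-4.3, and state that Total includes it. The grade grid goes from 5 x 4 to 5 x 5: five more cells per parameter, four of them new-onset.
2. Take the worst grade only from samples after first dose and up to 30 days after last dose, the limit that SAP 8.3 already uses for End of Treatment. Say that this settles the 30-day question left open in SAP 7.1. State a convention for samples dated on the day of first dose, because the laboratory listings show date and day but no time. Document the new window as a departure from Protocol 10.5.2.
3. Reconcile the visit label in SAP 8.3 and name one laboratory baseline for both the change and the shift tables, preferably the last non-missing value before first dose. Relabel the shells to match, and document the changed shift reference in the same departure.
4. If that baseline is adopted, show the Cycle 1 Visit 2 row of Table 14.3-2.2 as pre-dose or drop it. The change there would be zero by construction for patients with a Day 1 sample.

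The cost is wording in SAP 7.1 and 8.3, shell edits, re-derivation of the baseline and worst-grade variables, and repeat QC under SAP section 9. No new data are needed. Item 1 can be done alone if the sponsor prefers to keep the protocol's rule.

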6.1.2 Known Undesirable Effects of RAD001

Adverse events most frequently observed with RAD001 are rash, stomatitis/oral mucositis, fatigue, headache, anorexia, nausea, vomiting, diarrhea, ocular toxicity, and infections. Non-infectious pneumonitis has also been observed as indicated in [Section 1.2.3.3](#).

Overall, the most frequently observed laboratory abnormalities include neutropenia, thrombocytopenia, hypercholesterolemia, and/or hypertriglyceridemia. The majority of these AEs have been of mild to moderate severity (CTC grade 1 to grade 2). Refer to [Table 3](#) for management of laboratory abnormalities.

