7.6.5 Laboratory Evaluations

All standard clinical laboratory analyses described below are performed by local laboratories. The frequency of the assessments is indicated in Table 9. All laboratory procedures including collection of samples, shipment, reporting of results, alerting of extreme values, and notable values are provided in the Laboratory Manual. The local laboratory will provide the sponsor with a copy of the laboratory certification and tabulation of the reference ranges.

Abnormal laboratory values that are clinically relevant (i.e., require a dose modification, interruption, or indicate changes in previously abnormal values) must be recorded on the Adverse Events CRF page. For clinically relevant values from local laboratories, record actual laboratory abnormality value and grade on the local laboratory CRF page only if the severity grade is different from the severity grade reported by the local laboratory.

If a local laboratory value is recorded on the local laboratory CRF page, the site will provide the local laboratory reference range attached to the local laboratory CRF page.

All laboratory results must be available at the time the patient sees his/her attending oncologist.

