	N = xxxx
Overall (days)	
N	xx
Min	xx
Median	xx.x
Max	xx
Missing	xx
>0 to 4 months	xx (xx.x%)
>4 to 8 months	xx (xx.x%)
>8 to 12 months	xx (xx.x%)
>12 to 16 months	xx (xx.x%)
>16 to 20 months	xx (xx.x%)
>20 to 24 months	xx (xx.x%)
>24 months	xx (xx.x%)

Percentages are based on the number of patients in the Safety Population.
Source: Listing 16.2-3.1

Table 14.3-1.1 (page 1 of n)
 Normal Ranges for Hematology and Blood Chemistry Parameters

Parameter	Unit	Lab Number	Gender	Age Range	Lower Limit	Upper Limit
xxxxxxxxxxxxx	xx	xxxxx	Male	xx-xx	xx	xx
				xx-xx	xx	xx
			Female	xx-xx	xx	xx
				xx-xx	xx	xx
			Male		xx	xx
			Female		xx	xx
xxxxxxxxxxxxx	xx	xxxxx	Male		xx	xx
			Female		xx	xx
. . .						

Programming Note: Will need to confirm once ranges are available - if ranges are in SI units and hence do not vary across lab then the "lab number" column can be dropped.

Table 14.3-2.1 (page 1 of n)
 Summary Statistics of Hematology by Visit
 Population Safety

Visit	Statistic						
	n	Missing	Mean	SD	Min	Median	Max
Parameter: WBC (units)							
Baseline (N=xxxx)	xx	xx	xx.xx	xx.xxx	xx.x	xx.xx	xx.x
Cycle 1 Visit 2 (N=xxxx)	xx	xx	xx.xx	xx.xxx	xx.x	xx.xx	xx.x
Cycle 1 Visit 3 (N=xxxx)	xx	xx	xx.xx	xx.xxx	xx.x	xx.xx	xx.x
Cycle 2 Visit 4 (N=xxxx)	xx	xx	xx.xx	xx.xxx	xx.x	xx.xx	xx.x
Cycle 2 Visit 5 (N=xxxx)	xx	xx	xx.xx	xx.xxx	xx.x	xx.xx	xx.x
Cycle 3 Visit 6 (N=xxxx)	xx	xx	xx.xx	xx.xxx	xx.x	xx.xx	xx.x
Cycle 3 Visit 7 (N=xxxx)	xx	xx	xx.xx	xx.xxx	xx.x	xx.xx	xx.x
Cycle 4 Visit 8 (N=xxxx)	xx	xx	xx.xx	xx.xxx	xx.x	xx.xx	xx.x
Cycle 5 Visit 9 (N=xxxx)	xx	xx	xx.xx	xx.xxx	xx.x	xx.xx	xx.x
Etc.							
End of Treatment (N=xxxx)	xx	xx	xx.xx	xx.xxx	xx.x	xx.xx	xx.x

Source: Listing 16.3-1.1

Programming note: Table continues for all Cycles. Repeat for each hematology parameter in turn noting that absolute and percentage differentials need to be summarized separately. Results should be shown in SI units.

Table 14.3-2.2 (page 1 of n)
 Summary Statistics of Change from Baseline in Hematology by Visit
 Population Safety

Visit	Statistic						
	n	Missing	Mean	SD	Min	Median	Max
Parameter: WBC (units)							
Cycle 1 Visit 2 (N=xxxx)	xx	xx	xx.xx	xx.xxx	xx.x	xx.xx	xx.x
Cycle 1 Visit 3 (N=xxxx)	xx	xx	xx.xx	xx.xxx	xx.x	xx.xx	xx.x
Cycle 2 Visit 4 (N=xxxx)	xx	xx	xx.xx	xx.xxx	xx.x	xx.xx	xx.x
Cycle 2 Visit 5 (N=xxxx)	xx	xx	xx.xx	xx.xxx	xx.x	xx.xx	xx.x
Cycle 3 Visit 6 (N=xxxx)	xx	xx	xx.xx	xx.xxx	xx.x	xx.xx	xx.x
Cycle 3 Visit 7 (N=xxxx)	xx	xx	xx.xx	xx.xxx	xx.x	xx.xx	xx.x

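### SAP 8.3 gives no rule for deriving absolute neutrophils from a percentage differential, so percentage-only patients would be Missing in the neutrophil shift table

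*SAP*

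**What the plan says.** SAP 8.3 lists the hematology parameters. The first line applies to every patient: "White blood cells (WBC), hemoglobin, hematocrit, platelets". The differential then comes in one of two forms: "Either: absolute neutrophils, absolute lymphocytes, absolute eosinophils, absolute basophils and absolute monocytes" or the percentage equivalents, "Or: percentage neutrophils, percentage lymphocytes, percentage eosinophils, percentage basophils and percentage monocytes".

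The same section lists the parameters that receive a CTCAE v3.0 grade. For hematology these are "Hematology: WBC, hemoglobin, platelets and absolute neutrophils". The only conversion it describes is to SI units.

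In SAP 11, the programming notes to Tables 14.3-2.1 (by visit) and 14.3-2.2 (change from baseline) say that "absolute and percentage differentials need to be summarized separately". Shift Table 14.3-2.3 is produced only for parameters with a grade defined in the SAP text. It has Missing cells, and its percentages use patients with data at both screening and the later time point.

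Protocol 7.6.5 says: "All standard clinical laboratory analyses described below are performed by local laboratories". Protocol 10.5.2 promises shift tables by CTC grade.

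**The concern.** With local laboratories at 25 sites in eleven countries (protocol Table 10), mixed reporting formats are foreseeable, and the SAP provides for both. It then grades only one of them. The information needed to grade the other is already collected, but no rule tells the programmer to use it.

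Neutrophils are not a peripheral parameter here. Protocol 6.1.2 says that "the most frequently observed laboratory abnormalities include neutropenia, thrombocytopenia", and protocol Table 3 grades neutropenia on the absolute count. Table 14.3-2.3 is also the only planned summary table that would show neutropenia by grade. The adverse event table by preferred term (14.5-2.1) has no grade column, and protocol 10.5.2 leaves the CTC grades of adverse events to listings.

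A second effect concerns change from baseline. If a patient's reporting form differs between baseline and a later visit, Table 14.3-2.2 has no pair of like values to subtract.

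**Working it through.** The plan states no figure to reproduce; this is a question of data derivation.

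**Step 1. Is there a route from a percentage record to a grade?**
- Grading needs absolute neutrophils (SAP 8.3).
- A percentage record contains WBC and percent neutrophils (SAP 8.3).
- SI conversion changes units. It does not combine two variables.
- The shell notes treat the two forms as separate parameters.
- Neither document states a derivation.

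No route is specified.

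**Step 2. Can the percentage be graded by itself?** The identity is absolute neutrophils = WBC × (% neutrophils / 100). Protocol Table 3 puts grade 3 at below 1 and at least 0.5 × 10⁹/L, grade 4 at below 0.5, and grade 1 or better at 1.5 or above. With 30% neutrophils throughout:
- WBC 1.5: 1.5 × 0.30 = 0.45, grade 4
- WBC 3.0: 3.0 × 0.30 = 0.90, grade 3
- WBC 8.0: 8.0 × 0.30 = 2.40, above 1.5

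One percentage spans grade 4 to grade 1 or better, so the percentage alone cannot be graded. Percentage and WBC together can.

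**Step 3. How many patients?** The documents do not give the share with percentage-only differentials. I assume 10%, 25% and 50%, and take planned enrollment from protocol 4 (110) and SAP 3 (142).

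| Assumed share | Ungraded of 110 | Ungraded of 142 |
|---|---|---|
| 10% | 11 | 14 |
| 25% | 28 | 36 |
| 50% | 55 | 71 |

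**Step 4. How many grade 3 or 4 cases?** Missing cases = N × share × rate. The rate is also an assumption, taken as 5% to 10%.
- N = 110: from 110 × 0.10 × 0.05 = 0.6 to 110 × 0.50 × 0.10 = 5.5
- N = 142: from 142 × 0.10 × 0.05 = 0.7 to 142 × 0.50 × 0.10 = 7.1

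**Step 5. Does the derivation have a trap?** Protocol 7.6.5.1 counts bands as neutrophils. SAP 8.3 lets other differential counts be recorded but only lists them. Suppose a laboratory reports 40% neutrophils at WBC 2.0 with bands separate, and neutrophils plus bands come to 50%. Without bands, 2.0 × 0.40 = 0.80, which is grade 3. With bands, 2.0 × 0.50 = 1.00, which is not. The rule must therefore name bands.

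**The case against.** The strongest reply is that this is silence, not a prohibition. The SAP does not forbid deriving the count, and Listing 16.3-1.1 has a single Neutrophils row with a grade placeholder, which is compatible with grading every record. That is fair, and a reader who infers that these patients are certain to end up ungraded goes beyond the text. But a derivation left to the programmer is not pre-specified, and the shell notes point the other way.

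The number affected could be zero. Sites need an absolute count for eligibility (protocol 5.1) and for the Table 3 rules, so they may record it. This stands: the shares above are assumptions.

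Three stronger inferences are tempting, and the documents do not support them:
- *Neutropenia would go unrecorded.* Protocol 7.6.5 sends abnormal values that require dose modification or interruption to the Adverse Events page, and 7.6.1 requires severity grading. WBC is graded for everyone. The gap lies in the analysis and not in patient management.
- *The reported rate would be diluted or biased.* Shift percentages use patients with data, so Missing records do not dilute them. Bias needs reporting format to be related to neutropenia risk, which nothing in the documents shows.
- *A confidence interval would widen.* At an assumed 10% rate the 95% width would go from 2 × 1.96 × √(0.1 × 0.9 / 110) = 0.112 to 0.159 with 55 patients. No interval is planned for laboratory grades, so no planned output would change in this way.

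Protocol 6.1.2 also says that most of these events were mild to moderate, which limits how many high-grade cases are at stake. Finally, summarizing percentages separately by visit is an acceptable presentation choice and not an error.

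**Conclusion.** The gap is real and modest. Followed as written, the SAP leaves percentage-only patients without a neutrophil grade in Table 14.3-2.3 and outside the by-visit absolute-count summaries, although the data needed to include them are collected. The size depends on an unstated share: 11 to 55 of 110 patients, or 14 to 71 of 142, if that share is 10% to 50%. The absent grade 3 or 4 cases would number roughly 0.6 to 5.5, or 0.7 to 7.1, if the rate is 5% to 10%. What is lost is cases and completeness in one descriptive safety table, the only planned one that shows neutropenia by grade. The primary endpoint is not touched.

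**What to change.** In SAP 8.3, add that where only percentages are recorded, absolute neutrophils = WBC × (% neutrophils, plus % bands if reported separately) / 100, using WBC from the same sample. Then:
- grade reported or derived absolute counts, and use them in Table 14.3-2.3;
- include derived values in the absolute-count summaries of Tables 14.3-2.1 and 14.3-2.2, and amend the programming notes to say so;
- flag derived values in Listing 16.3-1.1.

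Percentage summaries may be kept or reduced to listings.

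The cost is one derivation rule and a flag, with no new data collection. The downsides are rounding in the derived value, and possible understatement of the count (hence too high a grade) where a laboratory separates bands but they were not recorded.
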